6.3.2 Time-to-First Occurrence Endpoints

The methodology in this section pertains to the following endpoints:

- 1. Time-to-SNF or IRF admission
- 2. Continuity of care
- 3. Time to ED visit

Analysis of these time-to-event endpoints will focus on estimation of the cause-specific hazard and thus will censor patients who die at the time of their death. Such an approach is suggested by

Austin, Lee, and Fine (2016) when the focus of the analysis is addressing etiologic questions and not prediction of individual patient prognoses.⁶ The method of Wei, et al. will be used as described in Section 6.3.1. We will also censor patients without continuous insurance coverage at the time of their first break in coverage. For Phase 2, participants who have not had one year of follow-up for claims are administratively censored at the last date for which claims were available, June 30, 2019.

When only a small number of patients experience death prior to observing the time-to-event endpoint of interest, the estimated covariate effects on the cause specific hazard will be highly similar to the estimated covariate effects on the subdistribution hazard associated with the time-to-event endpoint of interest that takes into accounting death as competing risk (using the Fine-Gray model).⁷ If more than 10% of patients experience death during the one-year follow-up period prior to observing the time-to-event endpoint of interest, we will supplement estimation of covariate effects on the cause specific hazard by estimating covariate effects on the subdistribution hazard using the Fine-Gray model. As noted in Section 6.3.1, correlation between event times with a hospital unit will be accounted for through use of a robust sandwich variance estimator for model parameters.

6.3.3 Recurrent Time-to-Event Analysis

The methodology in this section pertains to the following endpoints:

- 1. Time-to-All cause hospital readmission
- 2. Time-to-Recurrent Stroke

Analysis of these time-to-event endpoints will focus on estimation of the cause-specific hazard and thus will censor patients who die at the time of their death. The primary analysis methodology will make use of the PWP model⁸ and account for correlation between event times within a hospital unit through use of a robust sandwich variance estimator for model parameters. The PWP model only includes in the risk set for the (k+1)th event those patients who have had k events previously. If more than 10% of patients experience death during the one-year follow-up period we will supplement estimation of covariate effects on the cause specific hazard by estimating covariate effects on the subdistribution hazard using the approach of Fine and Gray in the context of the PWP model.

6.4 Approaches for Dealing with Missing Data

All analyses performed will make use of data only for COMPASS Study patients who are able to be linked with the claims database.

Data from the COMPASS Study indicate that several important baseline characteristics will be missing for 5-10% of patients.⁴ We will use multiple imputation by chained equations (MICE) to impute missing NIHSS, race, and other potential confounders as necessary. Primary and secondary endpoint analyses will be based on 100 imputed datasets. For each imputed dataset analysis procedures described above will be performed and the parameter estimates will be combined across imputed datasets using standard techniques. More details can be found in the COMPASS Study Phase I Statistical Analysis Plan to which this document is an addendum.

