3.2 Linkage Methodology

Given that the claims may not include direct patient identifiers that can be merged with study data, we need to develop a linkage methodology. We will document the proportion of records that were successfully linked by data source. Following is a description of the proposed methodology for each data source.

Medicare. The Medicare Master beneficiary Summary File will be linked with COMPASS patient data using iterative deterministic linkage protocols. Linkage variables will include: gender, date of birth, index discharge hospital, and date of discharge/dates of service. Dates will be allowed to match within +/- 3 days or on 2 of 3 date elements (day, month, and year). Such fuzzy matches will be reviewed and verified the presence of stroke-related ICD10 diagnostic codes in the claims and comparisons of Zip code information between COMPASS records and Medicare enrollment data.

BCBSNC. The BCBSNC claims will be linked with the COMPASS data using an iterative deterministic linkage protocol. Linkage variables will include patients' first name, middle name (initial) and last name, as well as patients' date of birth and gender. Manual review of matches will be conducted by two independent reviewers with discrepancies adjudicated by a third reviewer. Review of the possible linkages will include comparison of service dates (e.g., discharge date) and patient addresses available from the BCBS NC claims and the COMPASS data.

Medicaid. The North Carolina Department of Health and Human Services, as the custodian of the state Medicaid data, will perform the linkage of those data with COMPASS patient data, using as linkage variables patients' first name, middle name (initial) last name, date of birth and sex.

Mortality. COMPASS data will be linked to the North Carolina mortality data for the years 2016-2020 to obtain information on death up to 1 year following the index hospitalization discharge. A deterministic linkage of the mortality data with COMPASS data will be performed using name, address, sex, and date of birth as the identifier variables. Two independent reviewers will determine the matches and a third person will adjudicate differences.

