4.7 All-Cause Mortality

Deaths within 1 year of index discharge were ascertained from the North Carolina State Death Index as well as insurance claims beneficiary summary files. A death identified in either database will be considered a death.

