5 CLAIMS ANALYSES

5.1 Phase 1 Intent-to-Treat Analyses

We will perform intent-to-treat analyses comparing the COMPASS intervention to UC with respect to all endpoints listed in Table 1 stratified by insurance provider (i.e., FFS Medicare, NC Medicaid (excluding patients with dual Medicare coverage), BCBS-NC). Comparisons will be made based on the intervention arm to which a patient belongs regardless of whether the patient received any intervention. For intent-to-treat analyses, all individuals must have been enrolled at the time of the index discharge event in one or more of the insurers (CMS Medicare, NC Medicaid, or BCBSNC). The FFS Medicare analysis population will include participants enrolled in CMS Medicare Parts A & B. Participants only enrolled in Part A or those enrolled in Part C (Medicare Advantage) will be excluded. The Medicaid analysis population will include participants enrolled in a qualifying Medicaid plan. Examples of non-qualifying plans include plans only covering children, plans for pregnancy-related care, cancer-related care, or those covering emergency services only. Participants dually enrolled in Medicaid and Medicare will be excluded from the Medicaid analyses. The BCBS analysis population will consist of participants enrolled in BCBS of NC, not also enrolled in Medicare.

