5.2 Phase 2 Intent-to-Treat Analyses

We will perform intent-to-treat analyses comparing outcomes in Phase 2 to Phase 1 with respect to all endpoints listed in Table 1 stratified by insurance provider as described in Section 5.1. Phase 2 analyses will include an analysis of Sustainability that compares Phase 2 Sustainability to the Phase 1 Intervention phase. The analysis populations will be defined as above in Section 5.1 with the added requirement that the analysis is restricted to hospitals that were randomized to INV in Phase 1 and that delivered the COMPASS intervention per protocol to at least 1 participant in Phase 2 Sustainability. Phase 2 analyses will also include an analysis of pre-post comparative effectiveness that compares Phase 2 Intervention to Phase 1 Usual Care. This analysis is restricted to the set of hospitals that were randomized to Usual Care in Phase 1 and that delivered the COMPASS intervention to Phase 1 Usual Care in Phase 2.

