6.3 Analysis of Time-to-Event Endpoints

6.3.1 One-Year Mortality Analysis

Analysis of the one-year mortality endpoint will be performed using a Cox proportional hazards model that adjusts for the covariates described in Section 6.1. Analyses will be performed using the method of Wei, et al.⁵ which models the marginal distribution for event times and account for correlation between event times within a hospital unit through use of a robust sandwich variance estimator for model parameters.

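### The claims addendum limits 1-year mortality to claims-linked patients of three insurers, although its planned NC death linkage carries no insurer condition

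*SAP*

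**What the plan says.** Table 1 of the SAP lists time to death from any cause over one year, with a hazard ratio as estimand and claims plus the mortality index as source. On ascertainment, SAP 3.2 says "COMPASS data will be linked to the North Carolina mortality data for the years 2016-2020 to obtain information on death up to 1 year", matched on name, address, sex and date of birth. SAP 4.7 adds: "A death identified in either database will be considered a death".

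On population, SAP 5.1 plans the Phase 1 comparison "with respect to all endpoints listed in Table 1 stratified by insurance provider" and requires that "all individuals must have been enrolled at the time of the index discharge event in one or more of the insurers" (Medicare, NC Medicaid or BCBSNC). It excludes patients with Part A only, with Medicare Advantage or with a non-qualifying Medicaid plan. SAP 5.2 carries the same scheme into Phase 2: "comparing outcomes in Phase 2 to Phase 1 with respect to all endpoints listed in Table 1 stratified by insurance provider". SAP 6.4 closes the set: "All analyses performed will make use of data only for COMPASS Study patients who are able to be linked with the claims database".

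SAP 6.3.1, the mortality section, describes the model and the hospital-robust variance but names no other population: "Analysis of the one-year mortality endpoint will be performed using a Cox proportional hazards model that adjusts for the covariates described in Section 6.1".

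**The concern.** The utilisation endpoints in Table 1 need claims. Death is the one endpoint there that can be ascertained without them, because the state linkage uses identifiers from the COMPASS record. As written, the addendum looks up deaths in a source that does not depend on insurer and then analyses only patients who pass an insurer and linkage filter.

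Two things are at stake. The first is whom the estimate describes: patients of three payers, reported by payer, instead of the patients discharged home from the randomised hospitals. The second is precision, because each payer-specific hazard ratio rests on fewer deaths than were ascertained. The addendum gives no reason for applying the filter to death.

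**Working it through.** **1. Does any text exempt mortality?** Mortality is in Table 1. SAP 5.1 and 5.2 cover all of Table 1, SAP 6.4 covers all analyses, and SAP 6.3.1 sets no separate population. So there is no exemption. The patients left out are those with Medicare Advantage, Part A only, a non-qualifying Medicaid plan and no other qualifying cover, another insurer, no insurance, or a failed claims link.

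**2. Does another reading rescue it?** If the payer split means one model stratified by payer instead of separate analyses, patients outside the three insurers are still excluded. If the claims database in SAP 6.4 is read loosely to include the death index, the enrolment condition in SAP 5.1 still excludes them.

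**3. What does the protocol say?** It points both ways.
- Towards all patients: the Primary Study Question applies intention-to-treat to all primary and secondary outcomes. The Analytical Plan puts every stroke patient discharged home from a randomised hospital in those analyses.
- Towards claims: Secondary Aim 4 and the table of claims-linked outcomes name claims as the source for mortality.

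**4. Is an all-patient Phase 1 analysis feasible in time?** Protocol enrolment for Phase 1 ends in March 2018. Taking 31 March 2018 as the last discharge, 365 days of follow-up end on 31 March 2019, inside the 2016-2020 death data.

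**5. Size.** The plan gives no power, target hazard ratio, expected deaths, 1-year mortality or linked share for this endpoint, so there is no figure to reproduce. What follows is illustration under assumed values.

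Let f be the share of deaths retained. Without clustering, the standard error of the log hazard ratio rises by 1/√f.

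With clustering, assume 6,000 enrolled (the protocol's figure is for potentially eligible patients), 40 randomised units, m = 6,000/40 = 150 per unit, and the same f in every unit. Approximately, the inflation is √{[1 + (fm − 1)·ICC] / (f·[1 + (m − 1)·ICC])}. The full-cohort design effects are 1 + 149 × 0.005 = 1.745 and 1 + 149 × 0.01 = 2.49.

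| f (assumed) | No clustering | ICC 0.005 (assumed) | ICC 0.01 (assumed) |
|---|---|---|---|
| 0.90 | 1.054 | 1.031 | 1.022 |
| 0.75 | 1.155 | 1.091 | 1.064 |
| 0.60 | 1.291 | 1.175 | 1.125 |
| 0.50 | 1.414 | 1.253 | 1.182 |

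Example, f = 0.5 and ICC 0.005: √[(1 + 74 × 0.005)/(0.5 × 1.745)] = √(1.37/0.8725) = 1.253.

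These rows compare all patients with a pooled linked set. The addendum plans payer-specific estimates, where f is the payer's own share. At f = 0.25 the factor without clustering is 1/√0.25 = 2.

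**The case against.** The strongest defence has three parts. First, this is a claims addendum to a Phase 1 SAP that was not available, and SAP 6.2 cites full-cohort mortality at 90 days. An all-patient 1-year analysis may therefore exist elsewhere. This stands, and it confines the point to the addendum. Second, the protocol itself names claims as the mortality source, so a claims-based analysis is not a departure from it. That also stands: no available document specifies an all-enrolled 1-year hazard ratio that the addendum displaces. Third, SAP 3.1 limits claims to beneficiaries living in North Carolina, so the linked set suits a state death file and has a second death source. This is a defensible reason for a linked-patient analysis, but the addendum does not state it, and it does not rule out a second analysis.

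Three stronger readings are tempting but unsupported.
- A reader might infer that the Phase 2 claims cutoff also truncates mortality, since patients "are administratively censored at the last date for which claims were available, June 30, 2019". That rule is in SAP 6.3.2, which lists only SNF/IRF admission, continuity of care and ED visits. Mortality has its own section and a fixed one-year horizon.
- A reader might take the protocol's Analytical Plan to prescribe a single survival comparison across insurers. It speaks of models in the plural and names no insurance population. Secondary Aim 5, which asks for insurance status to be accounted for, can arguably be met by payer-specific analyses.
- A reader might conclude that the trial has no all-patient mortality result. The documents cannot show that.

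**Conclusion.** The point holds for the addendum. SAP 5.1, 5.2 and 6.4 limit 1-year mortality to claims-linked patients of three insurers, by payer, while SAP 3.2 provides a death linkage that needs no insurer. This sits poorly with the protocol's intention-to-treat statements, and the protocol is itself inconsistent on the mortality source.

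The loss of precision cannot be quantified from the documents. Under the assumed shares of 90% to 50% of deaths retained, a pooled linked estimate would have a standard error 1.05 to 1.41 times that of an all-patient estimate, and less with clustering. That is modest unless many deaths lie outside the linked set. The firmer consequence is the narrower population. This is a worthwhile, inexpensive improvement and does not invalidate the planned analyses.

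**What to change.** Exempt mortality from the restrictions in SAP 5.1 and 6.4. Add one Phase 1 Cox model of 1-year death in all enrolled, non-withdrawn patients, with these features:
- NC death-index ascertainment for everyone, so that detection does not depend on claims linkage;
- stratification by randomisation stratum, as in the protocol's Analytical Plan;
- the SAP 6.1 covariates plus insurance category from the enrolment data;
- the hospital-robust variance of SAP 6.3.1.

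Keep the claims-linked, payer-specific analyses with the either-source definition of SAP 4.7. Add a sensitivity analysis limited to patients with an NC home address. If the Phase 1 SAP already has an all-patient 1-year mortality analysis, cross-refer to it instead. In either case, reconcile the protocol's statements on the mortality source and the intention-to-treat population.

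The cost is SAP wording and one main model with its sensitivity analysis; the linkage is already planned. There are two downsides. Unlinked patients have one death source, so out-of-state deaths may be missed. Data-use coverage must also be confirmed first: the protocol's waiver text for claims and the Appendix 39 consent matrix describe linkage to claims and have no entry for state death data, so an IRB amendment could be needed. Because SAP 4.7 describes death ascertainment in the past tense, the added model should be dated and labelled as an addition.

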6.5 Subgroup Analyses

It is of *a priori* interest to examine the comparative effectiveness of the COMPASS Intervention in key subgroups of the studied population. We will examine the comparative effectiveness of the COMPASS Intervention in the following subgroups for the FFS analyses, where feasible:

- Diagnosis group stroke; TIA
- Race non-white; white
- Sex female, male
- Age -- <65; 65-<75; 75-<85; >=85
- NIHSS 0, 1-4, 5-15, and 16-42

Categories may be collapsed due to small sample sizes within each subgroup.

For each of the characteristic above (e.g., race) and to the extent that samples size permits, we will evaluate the comparative effectiveness of the COMPASS Intervention against usual care within each of the corresponding subgroups (e.g., for whites and non-whites) using the following procedure.

We will first assess the degree to which the data support the assumption of a homogeneous intervention effect across levels of each subgroup. This will be done by fitting an augmented model that includes a treatment by subgroup interaction and by formally testing the interaction at significance level 0.10. If the interaction is not statistically significant at level 0.10, the analyses adjusted for, but not stratifying by, subgroup will be presented for primary interpretation. However, if the interaction is significant at level 0.10, analyses will be presented that estimate separate treatment effects for each subgroup level using a single model with the familywise type I error rate controlled using Hommel's method.⁹

Bibliography

- 1. Agency for Healthcare Research and Quality (AHRQ). Clinical Classifications Software (CCS) for ICD-10-PCS (beta version). 2019; https://www.hcup-us.ahrq.gov/toolssoftware/ccs10/ccs10.jsp. Accessed Feb 15, 2021.
- 3. Centers for Medicare and Medicaid Services (CMS). Transitional Care Management Services. 2021; https://www.cms.gov/outreach-and-education/medicare-learning-network-mln/mlnproducts/downloads/transitional-care-management-services-fact-sheet-icn908628.pdf. Accessed Feb 15, 2021.

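### SAP 6.5 commits to subgroup-level effects only for factors that pass an unadjusted 0.10 interaction test, so the differences it displays are exaggerated, and the scope of its Hommel control is left unstated

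*SAP*

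**What the plan says.** SAP 6.5 (Subgroup Analyses) applies to the fee-for-service Medicare analyses, where feasible. It lists five factors: "Diagnosis group stroke; TIA"; "Race non-white; white"; "Sex female, male"; age in four bands; and NIHSS in four bands. Small categories may be collapsed.

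The procedure runs factor by factor: "For each of the characteristic above (e.g., race) and to the extent that samples size permits". The first step is an augmented model and "formally testing the interaction at significance level 0.10". The second step depends on the result:

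- Not significant: "the analyses adjusted for, but not stratifying by, subgroup will be presented for primary interpretation".
- Significant: the analysis will "estimate separate treatment effects for each subgroup level using a single model with the familywise type I error rate controlled using Hommel's method".

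The section gives no significance level for Hommel's method, does not define its family in so many words, and mentions no adjustment over the five interaction tests or over the nine endpoint rows of SAP Table 1. The Protocol's Analytical Plan also plans analyses by race, gender, age, stroke severity and insurance status, to judge whether the intervention effect is heterogeneous.

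**The concern.** The interaction test decides whether level-specific results are promised at all. That is reporting filtered by significance. A factor enters the display because its subgroups happened to look different, so the displayed differences are too large on average. A factor that fails leaves no committed estimate or interval from which a reader could see that the effects were similar, or merely imprecise. For subgroups declared of interest beforehand, the reader needs the estimates in both cases.

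The second issue is what the familywise statement covers. A reader who meets that word in a section on five factors may take it to cover all subgroup claims for an endpoint. The procedure, as most naturally read, corrects only over the levels of one factor.

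**Working it through.** SAP 6.5 states no error rate or power for subgroups, so there is no planned figure to reproduce.

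**Inputs from SAP 6.5 and Table 1.** Five factors with 2, 2, 2, 4 and 4 levels (14 in total); interaction level 0.10; nine endpoint rows. **Assumed.** Hommel level 0.05, with 0.025 and 0.10 as the range; global null; independent factors; normal level-specific estimates; no hospital clustering.

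**1. False interactions.** For one endpoint, P(at least one of five) = 1 − 0.9^5 = 0.41. Over all endpoints there are at most 5 × 9 = 45 tests, with 45 × 0.10 = 4.5 false positives expected. The 45 is a ceiling, because the section allows infeasible analyses to be dropped.

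**2. Exaggeration of what is shown.** Take a two-level factor with no interaction, so that the standardised difference z is standard normal. Without selection, E|z| = √(2/π) = 0.80. Given that it passes, E(|z| given |z| > 1.645) = 2φ(1.645)/0.10 = 2 × 0.1031/0.10 = 2.06. With a real difference, simulation gives:

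| True difference (SE) | Chance of passing | Mean shown difference ÷ truth |
|---|---|---|
| 1 | 26% | 2.2 |
| 1.5 | 44% | 1.6 |
| 2 | 64% | 1.3 |
| 3 | 91% | 1.06 |

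A real difference of 1.5 SE therefore leaves no promised level estimates in 56% of cases, and is overstated by about 60% in the rest.

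**3. Full procedure.** 200,000 simulated null trials per setting: heterogeneity chi-square test at 0.10 for each factor, then Hommel over that factor's levels. Hommel rejects at least one level exactly when the Simes test rejects. At Hommel level 0.05, over equal sizes, unequal sizes and NIHSS collapsed to three levels:

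| Quantity | Result |
|---|---|
| Any false level, one factor, without the interaction step | 5.0% |
| Same, with the interaction step | 2.9% to 3.6% |
| Any false level, given that the factor is displayed | 29% to 36% |
| Any false level over five factors, without the interaction step | 18% |
| Same, with the interaction step | 14.3% to 14.4% |

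The 18% lies below 1 − 0.95^5 = 22.6%, the value for fully independent families, because the five factors divide the same patients and share one overall effect.

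**4. Sensitivity to the Hommel level.** The last row becomes about 8% at 0.025 and about 23% at 0.10. The share of displayed factors with a false level becomes 16% to 20% and 49% to 59%. Steps 1 and 2 do not depend on the Hommel level.

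**5. Wider families.** One Hommel family over all 14 levels gives 3.8% to 4.0% per endpoint at 0.05. Pooling only over the levels of factors that passed does not help: about 13%.

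**The case against.** A reader might infer more than the documents support, in three ways.

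- **That the interaction step inflates the familywise error.** It does the reverse: it lowers the error from 18% to 14% over five factors and from 5% to about 3% within one. The excess over 5% comes from running five separate Hommel families. Selection harms the error among displayed factors and the size of the displayed differences.
- **That the familywise statement is false.** The text treats each characteristic in turn and applies Hommel within one model. Read so, the family is the levels of one factor, and control holds unconditionally. The SAP nowhere claims control over factors or endpoints, so 14% is the error of a wider family that the plan does not promise to control.
- **That subgroup results are suppressed when the test fails.** The section says what carries primary interpretation. It does not bar supplementary tables, and it opens by intending to evaluate effects within each subgroup. The gap is the lack of a commitment to report them.

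It can also be said that these endpoints are secondary, that testing interaction first suits a question about heterogeneity, and that the parent Phase 1 SAP, which was not supplied, may define the level or the family. All of this stands. It limits the error-rate point to one of clarification. It does not answer the selective display, which is written into 6.5 itself and holds however Hommel is read.

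**Conclusion.** The concern holds as a point about selective reporting and an undefined family. The rule commits to subgroup-level effects only after an unadjusted test at 0.10, gives a 41% chance per endpoint of at least one false interaction under the null, and makes displayed differences too large (2.06 SE against 0.80 SE for a two-level factor with no interaction). About 30% of displayed factors would carry a falsely significant level if Hommel runs at 0.05.

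The cross-factor error of about 14% per endpoint rests on the same assumed 0.05, with a range of about 8% to 23%. It measures what the Hommel step does not cover; it does not show that a stated property fails. All figures assume a global null except those for real differences in step 2. The simulated figures ignore clustering. The matter affects subgroup claims in the fee-for-service Medicare analyses and leaves the main treatment comparisons untouched.

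**What to change.** In SAP 6.5:

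1. For each endpoint where subgroup analysis is feasible, present the estimate and 95% CI for every analysed subgroup level, and the interaction p-value for all five factors, whatever the test shows.
2. State the Hommel level, state that it controls error only across the levels of one factor for one endpoint, and treat subgroup findings as exploratory. If the parent Phase 1 SAP already defines the level or family, cite it.

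A single Hommel family over all analysed levels of an endpoint is an alternative for a team that wants confirmatory subgroup claims. It is a choice, not a necessity, and fewer subgroup effects could then be called significant.

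The cost is a few lines of SAP text and longer tables, or one forest plot per endpoint. No new data are needed.
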